7.6.4 Personal Devices Data for Continuous Glucose Monitoring

It is noted that patients were allowed into the protocol whether they used personal CGM devices or did not previously use them. If they reported that they did use personal CGM devices, the sponsor obtained (separate) consent for obtaining the data from the personal device. These data may or may not be used for exploratory or supportive analyses.

7.6.5 Insulin Device Data

The following data extracted from devices will be of supportive interest:

Mean over the period of

- basal insulin (Prescribed Basal insulin is used)
- bolus insulin
- Number of boluses
- Total insulin (as a measure and adjusted by bodyweight)

7.6.6 Ketones and Glucose

Although beta-hydroxybutyrate (BOHB) is a safety analyte, protection from ketoacidosis is a potential benefit for TTP399 over other treatments for T1DM, which makes the subgroup analysis for potential efficacy a useful analysis. Subjects will be categorized on BOHB as follows:

- Negative: Trace ketone in urine and in serum less than 0.20 mmol/L (approximately 2 mg/dl)
- Mild: Plus one in urine or in serum 0.2 mmol/L (inclusive) – 0.29 mmol/L (inclusive) which is approximately 2 mg/dl – 2.9 mg/dl.
- Moderate high: Plus 2 in urine or in serum 30-40 mg/dl
- High: Plus 2 in urine or in serum 40-80 mg/dl (noninclusive)
- Marked high: Plus 3 in urine or in serum 80 mg/dl or more

Proportions of subjects will be analyzed for the following variables:

- Subjects with treatment-emergent abnormal values in BOHB
- Subjects with detectable ketones in urine beyond trace.
- Subjects with ketones in plasma or urine (TEAV in BOHB or detectable more than trace ketones in urine).

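### The five BOHB classes in SAP 7.6.6 leave a roughly tenfold serum range without a class and place urine 2+ in two classes

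*SAP*

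**What the plan says.** SAP 7.6.6 (Ketones and Glucose) presents protection from ketoacidosis as a possible advantage of TTP399 and then states: "Subjects will be categorized on BOHB as follows". Five classes come next. The lowest, Negative, requires urine no higher than trace together with a serum level under 0.20 mmol/L, which the SAP equates to roughly 2 mg/dl. The second class is given in both units: "Mild: Plus one in urine or in serum 0.2 mmol/L (inclusive) – 0.29 mmol/L (inclusive) which is approximately 2 mg/dl – 2.9 mg/dl". From the third class on, only mg/dl is used, and that class reads "Moderate high: Plus 2 in urine or in serum 30-40 mg/dl". The fourth repeats the urine grade of the third with a higher serum band: "High: Plus 2 in urine or in serum 40-80 mg/dl (noninclusive"). The fifth, Marked high, takes urine 3+ or any serum level from 80 mg/dl upwards.

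Negative joins its urine and serum conditions with 'and'; the other four use 'or'. The section gives no order of precedence and no rule for urine and serum that disagree, and the protocol does not define these classes.

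Below the classes, the same section lists three variables to be analysed as proportions: treatment-emergent abnormal values (TEAVs) in BOHB, urine ketones beyond trace, and the combination of the two ("Subjects with ketones in plasma or urine (TEAV in BOHB or detectable more than trace ketones in urine").

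**The concern.** A scheme that sorts every subject should give each of them exactly one class. This one fails in both directions: some combinations of urine and serum meet no class, and others meet two or three. Two programmers working from the text could produce different tables, and someone would have to supply the missing class and a tie-break. If that were done after unblinding, it would be a choice made with the data in view, on a property that the SAP presents as a possible benefit of the drug.

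**Working it through.** **Inputs.** All class limits are from SAP 7.6.6. The conversion is the SAP's own: 0.20 mmol/L is about 2 mg/dl, so 1 mmol/L is about 10 mg/dl. As a sensitivity check I also use 10.41 mg/dl per mmol/L. That assumes a molar mass of 104.1 g/mol for BOHB, a figure that is not in the documents.

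**Reproducing the SAP's figure.** 0.20 × 10 = 2.0 and 0.29 × 10 = 2.9 mg/dl, which matches the range stated for Mild. With 10.41 the limits are 2.08 and 3.02 mg/dl. The stated conversion is sound.

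**The gap.**

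| Quantity | Factor 10 | Factor 10.41 |
|---|---|---|
| Upper limit of Mild, 0.29 mmol/L | 2.9 mg/dl | 3.02 mg/dl |
| Lower limit of Moderate high, 30 mg/dl | 3.0 mmol/L | 2.88 mmol/L |
| Ratio of the two limits | 30 / 2.9 = 10.3 | 2.88 / 0.29 = 9.9 |

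The range without a serum class is about tenfold under either factor. The other limits, 40 and 80 mg/dl, are 4.0 and 8.0 mmol/L (factor 10) or 3.84 and 7.68 mmol/L (factor 10.41).

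**Applying the rules as written.** The table uses factor 10, takes trace to include no ketones, and takes the noninclusive note under High to refer to 80 only. Neg = Negative, MH = Moderate high, H = High, MkH = Marked high.

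| Urine | Serum 1 mg/dl | 2.5 | 5 | 29 | 35 | 40 | 60 | 90 |
|---|---|---|---|---|---|---|---|---|
| Trace or none | Neg | Mild | no class | no class | MH | MH, H | H | MkH |
| 1+ | Mild | Mild | Mild | Mild | Mild, MH | Mild, MH, H | Mild, H | Mild, MkH |
| 2+ | MH, H | Mild, MH, H | MH, H | MH, H | MH, H | MH, H | MH, H | MH, H, MkH |
| 3+ | MkH | Mild, MkH | MkH | MkH | MH, MkH | MH, H, MkH | H, MkH | MkH |

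Four results follow.

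1. Serum in the gap with urine at trace or below meets no class. Serum of 10 and 15 mg/dl gives the same result as 5 and 29.
2. Serum in the gap with urine 1+ is Mild, up to 29 mg/dl, which is 29 / 2.9 = 10 times the serum ceiling of that class.
3. Urine 2+ meets Moderate high and High at every serum value. Serum of exactly 40 mg/dl meets both on the reading above; if the noninclusive note also covers 40, that particular overlap goes.
4. Discordant pairs can meet several classes. Urine 1+ with serum 60 mg/dl is both Mild and High.

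**The case against.** The strongest reply is that nothing of consequence rests on these classes, and most of it stands. The three proportion variables in SAP 7.6.6 use the TEAV or urine beyond trace. The secondary variables in SAP 6.1.2 use the same criteria. The responder definition in SAP 6.1.1 uses the normal reference range for serum BOHB, and the version in SAP 5.3 uses the TEAV. No hypothesis in SAP section 2 involves a BOHB class. Diabetic ketoacidosis has its own definition and independent adjudication in Protocol 9.8.3. The list of displays in SAP section 11, which is not exhaustive, names no table of BOHB classes.

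A reader might infer that the trial's ketone results would understate ketosis. The documents do not support that. A subject with serum in the gap still counts in the TEAV proportions if the value is a TEAV. Because urine and serum are joined by 'or', urine of 1+ or more still yields a class. The double class for 2+ makes the counts ambiguous but hides no ketosis. The SAP does not say that unclassified subjects would be left out of the table, and the documents give no basis for estimating how many there would be.

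A reader might also infer that the upper limits are simply ten times too high. Read as 3 to 4, 4 to 8, and 8 mg/dl or more (0.3, 0.4 and 0.8 mmol/L at factor 10), they would adjoin the Mild class and the gap would largely close. A unit or decimal slip is therefore possible, but the documents do not confirm it. Protocol Table 2 and Appendix 2 list ketones and beta-hydroxybutyrate without units. Even on that reading, the duplicated 2+ and the discordant pairs would remain.

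**Conclusion.** The point holds, and it is minor. As written, the five classes are neither exhaustive nor mutually exclusive. Serum from above 0.29 to below about 2.9 to 3.0 mmol/L has no class of its own, urine 2+ has two, and discordant urine and serum can meet several. The conclusion rests on the SAP's own limits and conversion; the assumed molar mass moves the width of the gap only from 10.3-fold to 9.9-fold. Within the five-class display, some subjects would be unplaced and some with urine 1+ would be graded low for their serum value. The damage stops at that display.

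**What to change.** Before unblinding, amend SAP 7.6.6 to:

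- state every serum cut-point in one unit;
- reconcile the 30, 40 and 80 mg/dl limits with the 0.20 and 0.29 mmol/L limits, with the sponsor confirming which values were intended;
- make the classes contiguous and non-overlapping, with each boundary marked as included or excluded;
- give each urine grade one class;
- assign a subject whose urine and serum disagree to the worse of the two classes.

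The cost is a short SAP correction and the matching programming specification. Data collection, sample size and the other analyses do not change.

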7.6.7 Interim Analysis

The study protocol includes accommodation for an interim analysis, which may or may not be done as a business decision. If interim analysis is done, details of the plans for this interim analysis will be described in an interim analysis plan, which will include intentions for disclosure and plans to protect the integrity of the ongoing study. The goal is to support the adaptive trial design for optimization of the scientific conclusions that can result from this study.

This study conforms to regulatory guidance depicted in FDA adaptive design guidance FDA guidance Adaptive Design for Clinical Trials for Drugs and Biologics (draft guidance, February 2010) and also the European Medicines Agency guidance Reflection Paper On Methodological Issues In Confirmatory Clinical Trials Planned With An Adaptive Design (October 2007).

7.6.8 Subgroup Analysis

6.5.7.1. Randomization Stratification Subgroups

Part 2 of the study includes stratified randomization with two strata:

- Patients currently on CGM with at least 2 months of experience with personal CGM without significant interruptions (i.e. > 2 consecutive weeks) prior to screening who agree to continue using their personal CGM throughout the study in addition to the Sponsor supplied CGM.
- OR patients currently not using a personal CGM prior to screening who agree not to use a personal CGM during the study

Subgroup analysis will be done for each stratum separately and combined across strata.

6.5.7.2. Subgroups defined by Age at Onset

Age at onset of TID will be used for subgroup analysis of subjects with earlier age at onset.

- Subjects with Age at Onset less than 21 years
- Subjects with Age at Onset 21 years or more

It is noted that late onset (age 40 years or more) was prohibited per the protocol; consequently, it is unnecessary to specify that subgroup as of interest.

6.5.7.3. Subgroups defined by Entry HbA1c cut at 8%

Subjects with lower HbA1c are more likely to have insulin dose reductions with TTP399 under assumptions of the mechanism of action. A subgroup analysis will be done for two subgroups:

- Subjects with Baseline HbA1c less than 8%
- Subjects with Baseline HbA1c 8% or more.

6.5.7.4. Subgroups defined by use of InPen versus Pump

Use of the InPen or not will be used for subgroup analysis.

- Subjects who use InPen
- Subject who use a pump.

6.5.7.5. Subgroups defined by Use of InPen calculator

Patients who use the InPen calculator may have a different insulin profile than those who do not. This variable will be used for subgroup analysis.

- Subjects who use InPen and use the calculator
- Subjects who use InPen and to do not the calculator
- Subjects who use a pump

6.5.7.6. Subgroups defined by C-peptide detectable or not at baseline.

Patients who have quantifiable levels of C-peptide at baseline are of particular interest. It is noted that the assay used for this study has a limit of quantitation for C-peptide of

0.004 ng/ml. Statistical analysis will be done on HbA1c in this subgroup and also on change in C-peptide.

- Subjects with baseline C-peptide is less than 0.004 ng/ml
- Subjects with baseline C-peptide is at least 0.004 ng/ml.

6.5.7.7. Subgroups defined by baseline bodyweight

Patients who have low bodyweight at entry may differ from those who are heavier at entry. Subgroup analysis defined by baseline bodyweight will include analysis of HbA1c changes and also changes in bodyweight.

- Subjects with baseline bodyweight 85 kg or more
- Subjects with baseline bodyweight less than 85 kg.

7.7 Analysis of Safety Data

7.7.1 Adverse Events

Adverse events reported in this study will be coded using MedDRA®, Version 21.0 or later. Coding will be to the lowest level terms (LLT). The verbatim text, the preferred term, and the primary SOC will be listed in subject listings. Summaries that include frequencies and proportions of subjects reporting AEs will include the preferred terms and the SOCs.

Adverse event summaries will be done by study phase: (1) pre-dose,(2) placebo run-in, and (3) double-blind treatment phase, (4) period beginning with the first dose of double-blind medication, including follow-up phase. The final category is considered the primary summary of TEAEs to support comparisons of TTP399 with placebo.

Adverse events summaries will be constructed displaying AEs in decreasing order of total frequency according to the numbers of subjects reporting the AE (not the number of reports).

- Number (percent) of subjects reporting TEAE by Treatment and overall in accordance.

A listing will be constructed that includes the subject identification, the dose group, TEAEs, MedDRA terms, seriousness, severity, causality related to study medication, causality related to insulin, elapsed time to onset, duration, and outcome.

Adverse events of special interest (AESI) will include diabetic ketoacidosis and hypoglycemia.

For purposes of analysis and reporting, hypoglycemia events will be limited to those in the first two categories (severe hypoglycemia and documented symptomatic hypoglycemia) in accordance with FDA's regulatory guidance *Guidance for Industry Diabetes Mellitus: Developing Drugs and Therapeutic Biologics for Treatment and Prevention* (CDER, February 2008).

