9.8.2. Documenting and Reporting of Hypoglycemia

Hypoglycemia is of special concern in this population and should be described to the patients. Home glucose monitoring must be undertaken in the event patients experience symptoms of hypoglycemia. Patients should be instructed on self-management of a hypoglycemic episode (e.g., prompt ingestion of carbohydrates).

For the Sentinels, any episode of hypoglycemia associated with symptoms must be captured on the patient's diary and in the EDC as an AE with symptoms and contemporaneous glucose measurements if they are available.

For Part 1 and Part 2, hypoglycemic adverse events will be assessed and reported in three categories:

- **severe hypoglycemia** (**each** of the following criteria **must** be met):
 - The patient was unable to treat him/herself, requiring the assistance of another person to actively administer carbohydrate, glucagon, or other resuscitative actions. Neurologic impairment must be the explanation for why the patient could not treat him/herself and required the assistance of another person.
 - Blood glucose:
 - If blood glucose was measured and was ≤ 49 mg/dL (2.7 mmol/L) using plasma referenced- home glucometers, CGM (or central laboratory), **or**
 - If blood glucose was not measured, the clinical manifestations were reversed by oral carbohydrates, subcutaneous glucagon, or intravenous glucose.
- **documented symptomatic** hypoglycemia if typical symptoms **are** accompanied by measured glucose ≤ 70 mg/dL using plasma-referenced home glucometers (or central laboratory) or
- **probable symptomatic** hypoglycemia if typical symptoms are not accompanied by a glucose determination as described above but are presumably caused by a plasma concentration ≤ 70 mg/dL.

Treatment should be discontinued for a patient following an episode of severe hypoglycemia, if in the investigator's judgment the episode was both:

- unexpected with no substantial aggravating issues precipitating the episode
- unavoidable in the future, through dose adjustments of insulin and patient education.

Episodes of severe hypoglycemia will be evaluated by an independent data monitor in Part 1

and Part 2.

- Events that do **not** meet the criteria for severe hypoglycemia will be characterized as mild or moderate in severity.

Reporting of Hypoglycemia

Hypoglycemia will be reported following the classification published by the International Hypoglycaemia Study Group⁶ as follows:

Severe hypoglycemia (level 3):

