6.1.2 Secondary Efficacy

Secondary variables of analysis include:

- Achievement of no more than trace ketones in urine post-treatment
- Achievement of no treatment-emergent abnormal value in serum BOHB
- Achievement of no more than trace ketones in urine or treatment-emergent abnormal value in BOHB in serum
- Change from baseline relative to:
 - Time in target glycemic range (70-180 mg/dL);
 - Time in hyperglycemic range
 - Level 1 > 180 mg/dL
 - Level 2 > 250mg/dL
 - Time in hypoglycemic range
 - Level 1 < 70mg/dL
 - Level 2 < 54 mg/dL
- Change from baseline in average daily number of units of bolus insulin dose
- Percent change from baseline in average daily insulin dose
- Achievement of a decrease of at least 0.3% in HbA1c at Week 12 (responders)

Additionally, analysis will be done on hypoglycemia both thresholds (54 mg/dl and 70 mg/dl) using the following variables:

- Change from baseline (2-week period) to Week 12 (2-week period) on the number of hypoglycemia episodes
- Proportion of patients with at least one more treatment-emergent episode of hypoglycemia at Week 12 (2-week period) relative to baseline (2-week period).
- Time-adjusted change from baseline on the number of hypoglycemia episodes.
- Proportion of patients with at least one more time-adjusted treatment-emergent episode of hypoglycemia at Week 12 than at baseline.

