6.2.1 Treatment-emergent Adverse Events

A treatment-emergent adverse event (TEAE) is one that was not present at before the first dose of study medication in each period or represents the exacerbation of a pre-existing condition. It is noted that AEs that emerge during the placebo-run-in phase will be captured and reported separately from AEs that emerge during the double-blind-treatment period.

Safety variables of analysis include description of the following:

- Patients with TEAEs by Preferred Term (PT)
- Patients with TEAEs by system organ class (SOC) and PT within SOC
- Patients with any hypoglycemic TEAE by PT
- Patients with any severe TEAE
- Patients with any serious TEAE
- Patients with any related TEAE
- Patients with TEAEs that result in termination from the study

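### Hypoglycemia adverse events are summarized only as patients with at least one event, so the one planned source covering all 12 weeks is insensitive to a change in event rate when most patients have an event

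*SAP*

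**What the plan says.** Protocol 9.8.2 states that in Parts 1 and 2 "hypoglycemic adverse events will be assessed and reported in three categories": severe, documented symptomatic (symptoms with a measured glucose of 70 mg/dL or less) and probable symptomatic. SAP 7.7.1 names hypoglycemia an adverse event of special interest (AESI) and says that for analysis "hypoglycemia events will be limited to those in the first two categories".

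The analysis variable, in SAP 6.2.1, is "Patients with any hypoglycemic TEAE by PT". SAP 7.7.1 tabulates the number and percent of subjects with each event, in descending frequency "according to the numbers of subjects reporting the AE (not the number of reports". Individual events appear in a listing with onset and duration. SAP 7.7.2 names three sources for detecting hypoglycemia but no summary measure. SAP section 11 lists an AESI summary without saying what it will show.

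SAP 6.1.2 does plan episode counts: "analysis will be done on hypoglycemia both thresholds (54 mg/dl and 70 mg/dl) using the following variables". These include "Change from baseline (2-week period) to Week 12 (2-week period) on the number of hypoglycemia episodes" and "Time-adjusted change from baseline on the number of hypoglycemia episodes". Evaluations 5 and 6 in SAP section 2 test time below 70 and below 54 mg/dL.

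**The concern.** Documented symptomatic hypoglycemia can recur many times in an insulin-treated patient. A yes/no summary treats one episode and ten alike. If most patients in both arms have at least one episode, there is little room left for the percentages to differ, whether the drug raises or lowers the rate.

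That matters here because Protocol 1.1 presents the unmet need as tighter control and less insulin without more hypoglycemia. A similar percentage in both arms could be read as a similar burden when it is not, and a real reduction could be missed in the same way.

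The percentage also ignores time on drug. A patient who stops early has less time to record an event, so the crude figure tends to favor the arm with more early stopping. The documents give no dropout rate, so I have not sized this.

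**Working it through.** **The plan's own figures.** None concerns hypoglycemia. The stated sample sizes do reproduce. For HbA1c, 2(1.969 + 0.842)²/0.7² gives 33 per group by normal approximation, and an exact t calculation gives 80.9% power at 34. The 49 per group for 30% vs 60% responders reproduces with a continuity correction. Neither bears on this point.

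**Which source covers which weeks (Part 2).**
- Sponsor CGM: Weeks -2 to 0 and 10 to 12 only (Protocol 4.2). A patient who stops before Week 10 has no on-treatment sponsor CGM.
- Personal CGM: only some patients have it, and SAP 7.6.4 leaves its use optional.
- Insulin: bolus settings change on Day 1 and adjustment continues through the double-blind period (Protocol 8.11), so most of this falls outside sponsor CGM.
- Adverse-event record: the whole double-blind period, with start and end dates (Protocol 9.6).

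**Inputs.** 45 per arm (SAP 1.7, Table 1); 84 days (SAP 1.8); two-sided alpha 0.049 (SAP section 7). Assumed: placebo rate, dispersion k, and a true rate ratio of 2.

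**Formulas.**
- Mean events per patient: μ = rate × 84/365.25. For 13 per patient-year, μ = 2.99.
- Share with any event: 1 − (1 + kμ)^(−1/k), or 1 − e^(−μ) when k = 0.
- Power for the share: exact power of Fisher's test. The SAP names no test for adverse events, so this is only a yardstick.
- Power for the rate: SE of the log rate ratio = √{[(1/μ + k) + (1/(2μ) + k)]/45}; power = Φ(ln 2/SE − 1.969).

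Worked case, μ = 2.99, k = 1. Shares are 1 − 1/3.99 = 74.9% and 1 − 1/6.98 = 85.7%. SE = √[(1.334 + 1.167)/45] = 0.236. Power for the rate is Φ(0.693/0.236 − 1.969) = Φ(0.97) = 83%. Fisher power is 17%.

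| Placebo rate per patient-year | k | Any event, placebo vs doubled | Power, proportion | Power, rate |
|---|---|---|---|---|
| 0.2 | 1 | 4.4% vs 8.4% | 3% | 12% |
| 4 | 1 | 47.9% vs 64.8% | 27% | 68% |
| 13 | 0 | 95.0% vs 99.7% | 2% | 100% |
| 13 | 0.5 | 83.9% vs 93.7% | 18% | 97% |
| 13 | 1 | 74.9% vs 85.7% | 17% | 83% |
| 13 | 2 | 62.1% vs 72.2% | 12% | 59% |
| 13 | 4 | 47.3% vs 55.2% | 7% | 35% |
| 26 | 1 | 85.7% vs 92.3% | 8% | 87% |

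Read in reverse, the rows describe a halving: a placebo rate of 26 cut to 13 at k = 1 moves the share from 85.7% to 74.9%, with the same powers.

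**Size of the rate test.** In simulations (4,000 trials per setting, 45 per arm), a Wald test with moment-estimated dispersion had type I error of 4.9–6.0% at k = 0.5–1, 5.7–6.3% at k = 2 and 6.8–7.6% at k = 4. Simulated power at k = 4 was about 41%.

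**The case against.** The strongest reply is that the adverse-event table is not the trial's only view of hypoglycemia. SAP 6.1.2 plans counts and time-adjusted counts at both thresholds, Evaluations 5 and 6 test time below range, Protocol 9.8.2 counts level 2 CGM events, and SAP 8.2 keeps all CGM data for evaluating hypoglycemia events. This stands. A reader might infer that a doubled hypoglycemia rate would go unseen in the trial, and the documents do not support that. What remains is narrower. SAP 6.1.2 does not name its data source, and CGM is only an inference from the thresholds and the 2-week periods. If that inference is right, the counts miss most of Weeks 0 to 10 and do not separate symptomatic or severe events.

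A reader might also infer that the SAP rules out event counts. It does not: the phrase about reports sets the order of the general table, and the content of the AESI summary is unspecified. But an unspecified display does not replace the patient-count variable set in SAP 6.2.1.

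Two further points stand. The rates and dispersion are assumptions, and at k = 4 only about half the patients have an event: saturation is weak and the rate comparison itself is modest. And full episode-level reporting in Part 2 is not assured. The explicit rule in Protocol 9.8.2 to capture any symptomatic episode is written for the Sentinels, and the Part 2 phone contacts ask specifically about extreme episodes. If mainly those are entered, rates will be low and the percentage will not saturate.

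**Conclusion.** The point holds for the adverse-event comparison. Severe plus documented symptomatic hypoglycemia is reduced to yes/no, without counts or time on drug, in the only planned source that spans all 12 weeks.

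At an assumed 13 events per patient-year and k from 0 to 4, a doubling moves the percentage by 5 to 10.8 points. Power is 2–18% for the proportion against 35–100% for the rate. The rate comparison is the more sensitive at every setting examined, but its advantage shrinks as dispersion grows.

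The argument does not extend to severe hypoglycemia alone if it is rare: at 0.2 per patient-year nothing saturates and power is 3% against 12%. The planned tables are descriptive, so this is a loss of information in a safety summary and not an error in a formal test.

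**What to change.** Keep the patient-count table. In SAP 7.7.1/7.7.2, specify for the AESI summary, by arm:

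1. The number of events and events per patient-year, for severe plus documented symptomatic hypoglycemia and for documented symptomatic alone.
2. A rate ratio with 95% CI from a negative binomial model with log time as offset.
3. The counting window, with the offset matched to it: double-blind treatment, or through follow-up if those events are counted. This needs stating because SAP 7.1 keeps follow-up assessments out of the safety analysis, while the main adverse-event summary in SAP 7.7.1 includes follow-up.

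Report this beside the patient proportion as a supportive safety estimate.

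The cost is SAP wording and one model, since event dates (Protocol 9.6) and treatment duration (SAP 7.4) are already recorded. There are three drawbacks. Each episode must be entered as a separate report, so sites need that instruction and the estimate partly reflects reporting habits. A few frequent reporters widen the interval. The Wald interval is somewhat too narrow when dispersion is high. No dose or clinical rule changes.
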